5.2. SAFETY ANALYSIS SET

The safety analysis set (SAF) will be the same as ENR i.e., include all subjects who provided informed consent and received at least one ¹⁸F-AV-1451 injection.

This analysis set will be used to summarize demographic and other baseline characteristics (refer to Section 10), medical/surgical history, concurrent medical conditions/diseases, family neurological disease history, and subjects neurological disease history (refer to Section 11), concomitant medications (refer to Section 12), cognition assessments at screening (refer to Section 13), exposure to ¹⁸F-AV-1451 (refer to Section 14), and all safety data (refer to Section 16). Summaries will be presented overall and by most recent neurological disease diagnosis.

5.3. MODIFIED INTENT-TO-TREAT ANALYSIS SET

The modified Intent-to-Treat analysis set (mITT) will include all SAF subjects (refer to Section 5.2) recruited under this protocol with available PET Scan visual interpretation data (regardless of PET Scan image validity and evaluability)

This analysis set will be used to conduct the secondary efficacy analysis for the inter-reader agreement among readers (refer to Section 15.2.2). Summaries will be presented according to the individual reader's interpretation of the ¹⁸F-AV-1451 PET image (see Section 3.2 and APPENDIX 1).

5.4. FULL ANALYSIS SET

Two full analysis set (FAS) will be defined for this study, one for each primary efficacy analysis (refer to Section 15.1).

Document:	\\quintiles.net\enterprise\Apps\sasdata\SASa\sas\AVID\18F-AV-1451\Biostatistics\Documentation\SAP\Avid_18F-AV-1451-A16_SAP_Final_v1.0_20180815.docx		
Author:	XXXXXXXXXX	Version Number:	Final, v1.0
		Version Date:	15Aug2018
Template No:	CS_TP_BS016 – Revision 3	Reference:	CS_WI_BS005
Effective Date:	01May2012		

5.4.1. FULL ANALYSIS SET #1

The FAS #1 (FAS1) will include all SAF subjects (refer to Section 5.2) recruited under this protocol that:

- came to autopsy, *including* the Front-Runner Cohort (i.e., including the first three subjects who came to autopsy),
- had valid and evaluable PET data (refer to Section 3.2), and
- had valid and interpretable autopsy specimens (refer to Section 3.3), where interpretability will be assessed for the Braak Stage.

This analysis set will be used to summarize the consensus panel’s assessment of each TS (refer to Section 15.1), conduct supportive analyses to the first primary efficacy analysis (refer to Section 15.1.1) and secondary analysis of majority of readers versus the NFT Score TS (15.2.1) as well as to conduct the exploratory efficacy analysis exception of the logistic regression model for the NIA-AA autopsy diagnosis TS (refer to Section 15.3). Data will be presented according to the individual reader’s interpretation of the ¹⁸F-AV-1451 PET image (see Section 3.2 and APPENDIX 1), majority of readers’ interpretation of the ¹⁸F-AV-1451 PET image (see Section 3.2 and APPENDIX 1) or by most recent neurological disease diagnosis, as appropriate.

5.4.2. FULL ANALYSIS SET #2

The FAS #2 (FAS2) will include all SAF subjects (refer to Section 5.2) recruited under this protocol that:

- came to autopsy, *including* the Front-Runner Cohort (i.e., including the first three subjects who came to autopsy),
- had valid and evaluable PET data (refer to Section 3.2), and
- had valid and interpretable autopsy specimens (refer to Section 3.3), where interpretability will be assessed for the NIA-AA autopsy diagnosis.

This analysis set will be used to conduct supportive analyses to the second primary efficacy analysis (refer to Section 15.1.2) and majority of readers secondary analysis for the NIA-AA autopsy TS (refer to Section 15.2.1) as well as to conduct the logistic regression model exploratory efficacy analysis for the NIA-AA autopsy diagnosis TS (refer to Section 15.3). Data will be presented according to the individual reader’s or majority of readers’ interpretation of the ¹⁸F-AV-1451 PET image (see Section 3.2 and APPENDIX 1), as appropriate.

5.5. EFFICACY ANALYSIS SET

Two EFF will be defined for this study, one for each primary efficacy analysis (refer to Section 15.1)

5.5.1. EFFICACY ANALYSIS SET #1

The EFF #1 (EFF1) will include all SAF subjects (refer to Section 5.2) recruited under this protocol that:

- came to autopsy *after* the Front-Runner Cohort (i.e., excluding the first three subjects who came

Document: \\quintiles.net\enterprise\Apps\sasdata\SASa\sas\AVID\18F-AV-1451\Biostatistics\Documentation\SAP\Avid_18F-AV-1451-A16_SAP_Final_v1.0_20180815.docx

Author: XXXXXXXXXX	Version Number: Final, v1.0
	Version Date: 15Aug2018
	Reference: CS_WI_BS005

Template No: CS_TP_BS016 – Revision 3
Effective Date: 01May2012

Copyright © 2012 Quintiles Transnational Corp. All rights reserved.

The contents of this document are confidential and proprietary to Quintiles Transnational Corp. Unauthorized use, disclosure or reproduction is strictly prohibited.

to autopsy),

- had valid and evaluable PET data (refer to Section 3.2), and
- had valid and interpretable autopsy specimens (refer to Section 3.3) , where interpretability will be assessed for the Braak Stage.

This analysis set will be used to summarize demographic and other baseline characteristics (refer to Section 10), medical/surgical history, concurrent medical conditions/diseases, family neurological disease history, and subjects neurological disease history (refer to Section 11), concomitant medications (refer to Section 12), cognition assessments at screening (refer to Section 13), exposure to ¹⁸F-AV-1451 (refer to Section 14), and other efficacy endpoint (refer to Section 15.4) as well as to conduct the first primary efficacy analysis (refer to Section 15.1.1) and majority of readers secondary efficacy for the NFT Score TS (refer to Section 15.2.1). Summaries will be presented according to the individual reader’s interpretation of the ¹⁸F-AV-1451 PET image (see Section 3.2 and APPENDIX 1), majority of readers’ interpretation of the ¹⁸F-AV-1451 PET image (see Section 3.2 and APPENDIX 1) or by most recent neurological disease diagnosis, as appropriate.

5.5.2. EFFICACY ANALYSIS SET #2

The EFF #2 (EFF2) will include all SAF subjects (refer to Section 5.2) recruited under this protocol that:

- came to autopsy *after* the Front-Runner Cohort (i.e., excluding the first three subjects who came to autopsy),
- had valid and evaluable PET data (refer to Section 3.2), and
- had valid and interpretable autopsy specimens (refer to Section 3.3) , where interpretability will be assessed for the NIA-AA autopsy diagnosis.

This analysis set will be used to conduct the second primary efficacy analysis (refer to Section 15.1.2) and majority of readers secondary efficacy analysis for the NIA-AA autopsy diagnosis (refer to Section 15.2.1). Summaries will be presented according to the individual reader’s or majority of readers’ interpretation of the ¹⁸F-AV-1451 PET image (see Section 3.2 and APPENDIX 1), as appropriate.

5.6. SENSITIVITY ANALYSIS SET

The sensitivity analysis set (SENS) will include all SAF subjects (refer to Section 5.2) recruited under this protocol that came to autopsy after the Front-Runner Cohort (i.e., excluding the first three subjects who came to autopsy) with an available PET Scan visual interpretation (regardless of PET Scan image validity and evaluability; refer to Section 3.2) and available pathological diagnosis (regardless of its interpretability; refer to Section 3.3).

This analysis set will be used to conduct supportive analysis to the primary and secondary efficacy analyses exception of the inter-reader agreement among readers (refer to Sections 15.1 and 15.2). Data will be presented according to the individual reader’s or majority of readers’ interpretation of the ¹⁸F-AV-1451 PET image (see Section 3.2 and APPENDIX 1), as appropriate.

Document: \\quintiles.net\enterprise\Apps\sasdata\SASa\sas\AVID\18F-AV-1451\Biostatistics\Documentation\SAP\Avid_18F-AV-1451-A16_SAP_Final_v1.0_20180815.docx

Author:	XXXXXXXXXX	Version Number:	Final, v1.0
		Version Date:	15Aug2018
		Reference:	CS_WI_BS005

Template No: CS_TP_BS016 – Revision 3
 Effective Date: 01May2012

Copyright © 2012 Quintiles Transnational Corp. All rights reserved.

The contents of this document are confidential and proprietary to Quintiles Transnational Corp. Unauthorized use, disclosure or reproduction is strictly prohibited.

6. GENERAL CONSIDERATIONS

Categorical data will be summarized by the number and percentage of subjects in each category. Continuous data will be summarized by descriptive statistics including n (number of subjects with available data), mean, standard deviation (SD), median, minimum, and maximum values.

6.1. REFERENCE START DATE AND STUDY DAY

Study Day will be calculated from the reference start date and will be used to show start/stop day of assessments and events.

Reference start date is defined as the date of the first ¹⁸F-AV-1451 injection (Study Day 1 is the day of the first injection).

- If the date of the event/assessment is on or after the reference start date, then:
Study Day = (date of event/assessment – reference start date) + 1.
- If the date of the event/assessment is prior to the reference start date, then:
Study Day = (date of event/assessment – reference start date).

In the situation where the event/assessment date is partial or missing, Study Day and any corresponding durations will be missing.

6.2. BASELINE

Unless otherwise specified, baseline is defined as the last non-missing measurement taken prior to reference start date and time, i.e. date and time of first ¹⁸F-AV-1451 injection, including unscheduled assessments. In case where the last non-missing measurement and the reference start date and time coincide, that measurement will be considered as pre-baseline, with the exception of the adverse events (AEs) and medications. AEs/medications commencing on the reference start date and time will be considered as post-baseline (i.e. treatment-emergent/concomitant).

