8.3. Safety Analysis

Safety vital signs measurements will be summarized by subject and by evaluation time point. Change from baseline (pre-dose time point) values will be determined and summarized.

Adverse events including injection site reactions will be summarized in terms of number and percentage of subjects experiencing an AE. The summary will be further broken down by system organ class (SOC) and preferred term using Medical Dictionary for Regulatory Activities (MedDRA) terms. Adverse events will also be presented by severity, relationship to treatment and seriousness. All subjects who experience SAEs or who discontinue due to AEs will be summarized.

Discontinuation

All subjects who discontinued participation prior to completing the study will be listed and their discontinuation reasons will be tabulated.

Vital Signs

Changes in vital signs from baseline will be summarized.

8.4. ¹⁸F-AV-1451 Image Analysis

¹⁸F-AV-1451 retention on PET images from subjects with valid autopsy data will be interpreted by visual examination as either

- Neocortical Uptake Not Consistent with an AD Pattern (AD-: no increased neocortical activity in any region or increased activity is isolated to the mesial temporal, anterolateral temporal or frontal region(s);
- Neocortical Uptake Consistent with an AD Pattern (AD+: increased neocortical tracer activity in the posterolateral temporal (PLT), parietal (including precuneus), or occipital region(s)); or
- Neocortical Uptake Consistent with an AD Pattern and with Likelihood of Disease Progression (AD++, which is a subset of AD+ (Neocortical uptake consistent with an AD pattern) where increased tracer activity is found in the parietal (including precuneus) region(s) regardless of uptake elsewhere, or in the frontal region in addition to PLT, occipital, or parietal region(s)).

For the purpose of testing the primary analyses, a scan interpretation will be considered positive (hypothesized to correspond to a B3 neuropathology score in Primary Analysis 1 and an NIA-AA score of high AD pathology in Primary Analysis 2) if the scan is interpreted as at least consistent with an AD pattern (AD+ or AD++). Details of the visual PET image review methods will be provided in the Blinded Read Manual.

Images will also be assessed quantitatively (semi-automated computerized measurement of SUVRs) for exploratory analysis purposes. Details of the analysis methods will be provided in the Quantitative Methodology Document.

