In order to control for the potential progressive change in tau deposition over time, cognitively impaired subjects for who death did not occur within nine months of the ¹⁸F-AV-1451 PET scan were given the opportunity to undergo a second ¹⁸F-AV-1451 PET scan and continue in the protocol at the Sponsor's discretion. In order to obtain a second PET scan before the nine month expiry date, it was recommended that the second scan be performed any time between six and nine months after the first scan. If the subject agreed to a second ¹⁸F-AV-1451 PET scan, screening assessments were not repeated with exception of any updates to the medical history/concurrent medications and an updated neurological disease diagnosis (according to best available information) which were collected at the time of the second ¹⁸F-AV-1451 PET imaging visit. If the subject subsequently came to autopsy, the data (neurological disease diagnosis and ¹⁸F-AV-1451 PET scan) from the second ¹⁸F-AV-1451 PET imaging visit (nearest to time of death) will be used in the analyses. Cognitively normal (unimpaired) subjects were not required to undergo repeat scans, even if death occurred more than nine months after the ¹⁸F-AV-1451 PET scan, because cortical tau deposition was expected to occur very slowly, if at all, in such subjects. That is, cognitively normal subjects remained eligible for autopsy, regardless of time from first or second scan to autopsy, and will be included in the Primary Efficacy Analysis Cohort if the subject came to autopsy at any time before the trial stopping criteria were met (refer to Section 7.1).

Up to the first 6 subjects that come to autopsy were to be considered as 'front-runners'. Avid were not blinded to the front-runner imaging and pathology results. These results were analyzed on a patient-by-patient basis and were used to refine the PET or autopsy methods (e.g., pathology staining, quantitation methods, etc.). Upon completion of the final front-runner subjects analysis, the final imaging and autopsy methods were specified. No additional PET image reads or autopsy analyses were performed until the PET image read and autopsy methods were finalized. The front-runners will not be included in the Primary

Document:	\\quintiles.net\enterprise\Apps\sasdata\SASa\sas\AVID\18F-AV-1451\Biostatistics\Documentation\SAP\Avid_18F-AV-1451-A16_SAP_Final_v1.0_20180815.docx		
Author:	XXXXXXXXXX	Version Number:	Final, v1.0
		Version Date:	15Aug2018
		Reference:	CS_WI_BS005

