6.3. REPEATS, UNSCHEDULED VISITS AND EARLY TERMINATION DATA

In order to control for the potential progressive change in tau deposition over time, cognitively impaired subjects for whom death did not occur within nine months of the ¹⁸F-AV-1451 PET scan were given the opportunity to undergo a second ¹⁸F-AV-1451 PET scan and continue in the protocol at the Sponsor's discretion. If the subject agreed to a second ¹⁸F-AV-1451 PET scan, screening assessments were not repeated with exception of any updates to the medical history/concurrent medications and an updated neurological disease diagnosis (according to best available information) which were collected at the time of the second ¹⁸F-AV-1451 PET imaging visit. If the subject subsequently came to autopsy, the data (neurological disease diagnosis and ¹⁸F-AV-1451 PET scan) from the second ¹⁸F-AV-1451 PET imaging visit

Document: \\quintiles.net\enterprise\Apps\sasdata\SASa\sas\AVID\18F-AV-1451\Biostatistics\Documentation\SAP\Avid_18F-AV-1451-A16_SAP_Final_v1.0_20180815.docx

Author: XXXXXXXXXX	Version Number: Final, v1.0
	Version Date: 15Aug2018
	Reference: CS_WI_BS005

Template No: CS_TP_BS016 – Revision 3
Effective Date: 01May2012

Copyright © 2012 Quintiles Transnational Corp. All rights reserved.

The contents of this document are confidential and proprietary to Quintiles Transnational Corp. Unauthorized use, disclosure or reproduction is strictly prohibited.

(nearest to time of death) will be used in the analyses. Cognitively normal (unimpaired) subjects were not required to undergo repeat scans, even if death occurred more than nine months after the ¹⁸F-AV-1451 PET scan, because cortical tau deposition is expected to occur very slowly, if at all, in such subjects. That is, cognitively normal subjects remained eligible for autopsy, regardless of time from first or second scan to autopsy. The safety analyses will include data from all scans.

This study does not accommodate unscheduled visits and no data will be collected at the time of an early termination beside the date and reason for discontinuation.

Listings will include scheduled, repeat, and early discontinuation data.

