16.4. VITAL SIGNS

Vital sign measurements (pulse rate, respiratory rate, and blood pressure) will be taken in the supine position at screening, immediately prior to the ¹⁸F-AV-1451 injection, and after completion of the imaging prior to discharge.

The change in vital sign measurements from baseline to completion of imaging prior to discharge will be computed as the value collected after the completion of the imaging prior to discharge minus the baseline value. Observed and change from baseline values will be summarized through use of descriptive statistics for the each ¹⁸F-AV-1451 injection.

Incidence of potentially clinically significant abnormal values will also be provided for each ¹⁸F-AV-1451 injection and a listing of subjects with potentially clinically significant abnormal values will be prepared.

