16.4.1. POTENTIALLY CLINICALLY SIGNIFICANT ABNORMAL VITAL SIGNS CRITERIA

Potentially clinically significant abnormal vital sign measurements will be identified in accordance with the following criteria:

Document:	\\quintiles.net\enterprise\Apps\sasdata\SASa\sas\AVID\18F-AV-1451\Biostatistics\Documentation\SAP\Avid_18F-AV-1451-A16_SAP_Final_v1.0_20180815.docx		
Author:	XXXXXXXXXX	Version Number:	Final, v1.0
		Version Date:	15Aug2018
Template No:	CS_TP_BS016 – Revision 3	Reference:	CS_WI_BS005
Effective Date:	01May2012		

Table 4 Potentially Clinically Significant Abnormal Vital Signs Criteria

Variable	Unit	Low	High
SBP	mmHg	≤ 90 mmHg AND change from baseline ≤ -20 mmHg	≥ 180 mmHg AND change from baseline ≥ 20 mmHg
DBP	mmHg	≤ 50 mmHg AND change from baseline ≤ -15 mmHg	≥ 105 mmHg AND change from baseline ≥ 15 mmHg
Pulse rate	bpm	≤ 50 bpm	≥ 110 bpm AND change from baseline ≥ 20 bpm
Respiratory rate	breaths/ min	≤ 10 breaths/min	NA

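### Vital-sign baseline is tied to the first injection, so changes after a second injection are measured against a value taken months earlier

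*SAP*

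**What the plan says.** SAP 6.1: "Reference start date is defined as the date of the first" injection. Nothing resets it at a second injection.

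SAP 6.2: unless another rule is given, baseline "baseline is defined as the last non-missing measurement taken prior to reference start date and time, i.e. date and time of first" injection.

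SAP 16.4: the change "will be computed as the value collected after the completion of the imaging prior to discharge minus the baseline value". It continues: "Observed and change from baseline values will be summarized through use of descriptive statistics for the each" injection. No injection-specific baseline is stated.

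SAP 16.4.1, Table 4, builds the change into its criteria. Low systolic pressure, for example, is "≤ 90 mmHg AND change from baseline ≤ -20 mmHg".

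SAP 6.3: "The safety analyses will include data from all scans". SAP 3.1 adds that "it was recommended that the second scan be performed any time between six and nine months after the first scan", and its footnote also allows an imaging visit to be repeated when the image is invalid.

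Protocol 8.3: "Change from baseline (pre-dose time point) values will be determined and summarized". It does not say which dose is meant. Protocol 7.1.2 has vital signs taken immediately before administration at an imaging visit, and Protocol 7.1.4 repeats the 7.1.2 procedures at a second scan. SAP 3.5 lists no departure from the protocol on this point.

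**The concern.** A pre- to post-imaging change in vital signs is meant to show the acute effect of the tracer. The SAP's treatment-emergent window for adverse events is 48 hours after an injection, which is the time scale of interest. For a second injection, the baseline in SAP 6.2 is instead a reading from before the first one, in people with terminal illness whose medical history and medications are updated at the second visit because they may have changed.

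At stake are the second-injection change summaries and the potentially clinically significant flags. Long-term decline could appear as an acute fall, and a real acute change could be hidden when blood pressure moved the other way between visits.

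**Working it through.** **Which baseline applies.** SAP 6.1 fixes the reference date at the first injection. SAP 6.2 uses it unless another rule is specified. SAP 16.4 specifies none and reports each injection. A programmer following these sections subtracts a pre-first-injection value from a post-second-injection value.

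**Age of that value.** With the 30.4375 days per month used in SAP 11.1, 6 × 30.4375 ≈ 183 days and 9 × 30.4375 ≈ 274 days.

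**What the change then contains.** Let B1 and B2 be the pre-dose values at the first and second injections and P2 the value after the second scan:

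P2 − B1 = (P2 − B2) + (B2 − B1).

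The first term is the acute change. The second is between-visit drift. If the two are independent, the variances add.

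**Table 4.** Five of the seven criteria use a change: systolic low and high, diastolic low and high, and pulse high. Pulse low and respiratory rate low do not.

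**Effect on the systolic flags.** The values below are illustrative (mmHg). Low requires a value ≤ 90 and a change ≤ −20. High requires a value ≥ 180 and a change ≥ 20.

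| B1 / B2 / P2 | Change from B1 | Flag as written | Change from B2 | Flag with same-visit value |
|---|---|---|---|---|
| 125 / 92 / 88 | −37 | low | −4 | none |
| 105 / 115 / 88 | −17 | none | −27 | low |
| 150 / 178 / 182 | +32 | high | +4 | none |
| 175 / 160 / 182 | +7 | none | +22 | high |

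Errors run in both directions.

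**Probability of a systolic change ≤ −20 mmHg (change component only).** The documents give no standard deviations, so these inputs are assumptions: acute change with mean 0 and SD 10; between-visit drift with mean m and SD s; normal approximation.

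- Same-visit baseline: Φ(−20/10) = 0.023.
- First-injection baseline: Φ((−20 − m)/√(10² + s²)).
  - m = 0, s = 12: Φ(−20/15.6) = 0.10
  - m = −5, s = 15: Φ(−15/18.0) = 0.20
  - m = −10, s = 15: Φ(−10/18.0) = 0.29
  - m = −10, s = 20: Φ(−10/22.4) = 0.33

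**Full low-systolic flag (both conditions).** A separate simulation of 2,000,000 subjects per setting used different assumptions: first pre-dose mean 120 and SD 18, acute SD 8, no acute effect.

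| Mean drift (mmHg) | First-injection baseline, between-visit SD 10 | First-injection baseline, between-visit SD 15 | Same-visit baseline |
|---|---|---|---|
| 0 | 2.4% | 5.5% | 0.2% |
| −5 | 5.1% | 9.1% | 0.3% |
| −10 | 9.6% | 14.0% | 0.3–0.4% |
| −15 | 16.3% | 20.4% | 0.4% |

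The mean change against B1 equals the drift. Against B2 it is 0. Even with no mean drift, the flag rate is more than ten times higher, because between-visit variability alone widens the change.

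**The case against.** SAP 6.2 leaves room for a different rule. SAP 16.4 lists a measurement just before injection, and Protocol 8.3 equates baseline with the pre-dose time point, so a same-visit baseline may well have been intended. The table shells, which SAP section 8 says describe the outputs, are not available and could settle it. The SAP is based on protocol amendment 3, whereas the protocol at hand is amendment 2. All of this bears on intent. None of it changes the written rule, because SAP 16.4 states no alternative.

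Other outputs limit the harm. Observed values are summarised for each injection, all eCRF data are listed, and clinically significant vital-sign findings are reported as adverse events, with treatment emergence tied to any injection plus 48 hours. A careful reader could therefore recover the acute change, but the change table and flags would still be misleading.

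The scope is narrow. Only subjects with more than one injection are affected, and the documents do not give their number. No statistical tests are planned for safety, and efficacy does not use this baseline. The gap of months applies to planned repeat scans; for a repeat after an invalid image no interval is stated.

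The 10% to 33% range covers the change condition only. The full flag also needs a systolic value of 90 or below, and under the simulation's assumptions its rate is 2.4% to 20.4%. That limit on the figures stands.

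**Conclusion.** The concern holds. As written, the SAP measures vital-sign change after a planned second injection against a value roughly 183 to 274 days old, although a same-visit pre-dose value is collected and is the natural reading of the protocol.

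Under the assumed inputs, a spurious systolic fall of 20 mmHg or more becomes several times more likely, and true acute changes can go unflagged. The size depends on assumed standard deviations and drift; the documents support neither a direction nor an amount. The consequence is confined to second-injection vital-sign summaries and five Table 4 criteria, so this is a correction that should be made, not a threat to the trial's conclusions.

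**What to change.** Add one sentence to SAP 6.2 or 16.4: for vital signs, baseline for each injection is the last non-missing value before that injection, normally the same-visit pre-dose reading, and this baseline also applies to the Table 4 criteria. Keep the first-injection definition for other baseline data. Settle it before database lock and unblinding, and check that the shells agree.

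The cost is that sentence and a small programming change. No new data are needed.
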